### **Sample Size**

For EFFECTIVENESS TRIAL:

This Randomized Controlled Effectiveness Trial is powered to detect differences on the two primary outcomes: (1) significantly reduced proportion of participants with an ER visit at the 3-month follow-up assessment (6 months post randomization) in the Living Well condition versus control, (2) significantly improved health functioning at post-treatment in the Living Well condition versus control as measured by the SF-12.

ER Visits. In our prior pilot the proportion with an ER visit in the Living Well condition at the 3-month follow-up was 10.7% and in the control condition it was 27.6%. For this power calculation we assumed that the proportion with an ER visit in the Living Well condition at the 3-month follow-up will be 10.7%. However, since we have an active control in this proposal, we specify a lower percentage in the control condition (versus estimate from the pilot study) equal to 25%, and thus a 14.3 percentage point difference. With a two-tailed, alpha .05 level test, and power = .80 to detect this 14.3 percentage point difference we calculate that we will need n = 250 (125 per condition). The percentage point difference that can be detected could be somewhat higher or lower depending on the inter-correlations among the covariates and ER response variable. As proportion with an ER visit will be obtained from VA electronic medical charts for all randomized participants, loss to follow-up is not a significant concern for this outcome. This calculation is conservative -- we would actually have power equal to .80 to detect a smaller difference because the above calculation is based on a basic z-test of proportions, whereas the analysis model

specified above is more powerful. Calculation was performed using PASS version 11.0 (from NCSS, LLC) software. We acknowledge that use of the ER may be different in the VA context given the co-location of medical and psychiatric care, but as evidenced in our previous work (see section A.3), we found that veterans with SMI used the VA ER for medical care at rates comparable to (even greater than) those in our community sample. Specifically, the rate of use in the VA sample was 43% and the baseline rate in the Living Well sample was 31.3%.

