For proportion with ER use in the past 6 months, we will use a random intercept mixed effects model since this outcome is assessed at only 2 time points. We will use a model that assumes no difference at randomization given the large sample size and randomization to study condition. Thus we will not include study condition as a main effect which would correspond to an assumption of unequal randomization rate of ER use. Some chance variation is expected and we will test the assumption of equal randomization rates with a chi-square test comparing the ER use rates by study condition. This model is equivalent to adjusting for randomization in the continuous case and we are taking this approach to be able to have .80 power to detect a smaller percentage point difference in ER use (50) at the 3 month follow-up assessment than if we didn’t assume equal rates at randomization. In the very unlikely scenario of a statistical difference at randomization we will add the study condition main effect to the model below, and the test of the null for H2 will continue to be the test that the coefficient for the study-condition-by-time interaction term is zero. To compare the two conditions on probability (p) of an ER visit, we let the outcome variable  $Y = 1$  if the participant had an ER visit in the prior 6 months (at randomization or at 3-month follow-up) and  $Y = 0$  if participant did not have an ER visit. Analysis model (logistic mixed effects model, random intercept not displayed) will be:

$$\text{logit}(E[Y]) = \text{Intercept} + \text{site} + \text{covariates} + \text{time} + \text{study-condition} \cdot \text{time}$$

where  $E[Y] = p = \text{probability participant has an ER visit in the prior six months at either randomization or 3 month follow-up (depending on “time” variable)}$ .

Notes: (1) Test of H2 will be the F-test that the coefficient for the study condition-by-time interaction is zero; (2) Study condition indicator main effect is omitted based on assumption of equal rates at randomization as discussed above; (3) For this hypothesis, “time” is a binary variable indicating assessment at 3 months post-treatment versus assessment at randomization; (4) The “covariates” terms represent adjustment for age, race, gender, Charlson comorbidity index score, chronic somatic illness category and other potential confounders found to be significantly different at randomization, (5) We have included a “site” term to adjust for site differences.

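### H2 changes model when a baseline test is significant: overall type I error rises modestly, but false positives reach about 18–26% in the roughly 1 trial in 20 where the rule fires

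*Protocol*

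**What the plan says.** The rule is in the Protocol, Data Analysis, under Hypothesis 2.

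- **Default model.** "We will use a model that assumes no difference at randomization given the large sample size and randomization to study condition". The logistic mixed model therefore has site, covariates, time and condition-by-time, but no condition main effect. Two reasons are given: "This model is equivalent to adjusting for randomization in the continuous case", and the approach is taken "to be able to have .80 power to detect a smaller percentage point difference in ER use".
- **Test.** "Test of H2 will be the F-test that the coefficient for the study condition-by-time interaction is zero".
- **Pre-test.** "we will test the assumption of equal randomization rates with a chi-square test comparing the ER use rates by study condition". Its significance level is not stated.
- **Switch.** "In the very unlikely scenario of a statistical difference at randomization we will add the study condition main effect to the model below". The interaction coefficient remains the test of H2 after the switch.

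The Sample Size section powers H2 at a two-sided .05 level and leans on the same analysis model when it says "we would actually have power equal to .80 to detect a smaller difference". Nothing is said about what the switch does to the error rate.

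**The concern.** Two things are wrong with the rule.

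First, the trigger is not a rare event that a large trial avoids. When allocation is random, any baseline difference is chance, and a significance test finds one at its own level whatever the sample size. At .05 that is 1 trial in 20.

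Second, the interaction means something different in the two models. Without the main effect, it is a follow-up comparison adjusted for baseline. With the main effect, it is a difference in change. If the arms differ by chance at baseline, they tend to move back together at follow-up, and a difference-in-change test counts that movement as treatment effect. The rule picks this test exactly when the chance difference is large.

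The model with the main effect is not invalid in itself; used in every trial it holds about 5%. The fault lies in selecting it because the baseline happened to be imbalanced.

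H2 is one of two primary outcomes. If the rule fires, the result depends heavily on which arm started higher by chance: Living Well starting higher produces spurious benefit, and Living Well starting lower hides a real one.

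**Working it through.** **1. The plan's own figure.** Inputs from Sample Size: 10.7% v 25%, two-sided .05, power .80. With mean proportion .1785 and d = .143:

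n = [1.96·√(2·.1785·.8215) + .8416·√(.107·.893 + .25·.75)]² / .143² = (1.061 + .448)² / .02045 = 111.4, so 112 per arm.

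With continuity correction: (111.4/4)·[1 + √(1 + 4/(111.4·.143))]² = 125 per arm. The stated 250 is reproduced with the correction. This does not bear on the switch; it fixes the setting.

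**2. Normal approximation under no effect.** Let B and F be the standardized arm differences at baseline and follow-up, with correlation r.

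- Default test: (F − rB)/√(1 − r²). Its covariance with B is r − r = 0, so it rejects 5% of the time whatever the baseline.
- Switched test: (F − B)/√(2(1 − r)). Its correlation with B is −√((1 − r)/2).
- Given B > 1.96, B averages φ(1.96)/.025 = .0584/.025 = 2.34, so the switched statistic is centred well away from zero.
- Overall error = .95 × .05 + .05 × (rejection rate where the rule fires, by numerical integration).

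The Protocol gives no correlation for ER use (its .50 belongs to the SF-12 calculation), so a range is shown.

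| r (assumed) | 0 | .27 | .5 | .6 | .8 |
|---|---|---|---|---|---|
| Centre of switched statistic, given B > 1.96 | −1.65 | −1.41 | −1.17 | −1.05 | −0.74 |
| False positives where rule fires | 33.8% | 25.2% | 18.5% | 15.7% | 10.3% |
| Overall type I error | 6.4% | 6.0% | 5.7% | 5.5% | 5.3% |

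For example, at r = 0: .0475 + .05 × .338 = .0644. Virtually all these errors favour the arm that started higher.

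**3. Simulation of the planned type of model.** 100,000 trials per setting, 125 per arm. Data are complete at both times, following Sample Size ("As proportion with an ER visit will be obtained from VA electronic medical charts for all randomized participants"). Baseline ER use is 31.3%; follow-up is 25% in both arms (no effect) or 25% v 10.7% (planned effect). Random-intercept logistic model, Wald test of the interaction, trigger at chi-square above 3.84, no site or covariate terms.

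| Within-person phi (assumed) | .15 | .27 | .45 |
|---|---|---|---|
| Rule fires (no effect) | 5.0% | 5.1% | 4.9% |
| **No effect, trials where it fires** | | | |
| Rejects after switch | 26.3% | 23.5% | 17.5% |
| Rejects if default kept | 4.8% | 5.0% | 5.0% |
| False benefit, Living Well higher, after switch | 25.6% | 24.0% | 18.1% |
| Same, default kept | 2.5% | 2.6% | 2.2% |
| **No effect, all trials** | | | |
| Error with the rule | 5.9% | 5.6% | 5.3% |
| Error, default always | 4.8% | 4.7% | 4.7% |
| Error, main effect always included | 4.9% | 4.8% | 4.7% |
| **Planned effect** | | | |
| Power where it fires: switch / default | 56% / 85% | 61% / 86% | 70% / 90% |
| Power, Living Well lower: switch / default | 15% / 84% | 22% / 86% | 41% / 90% |
| Overall power: rule / default | 83.7% / 85.2% | 85.4% / 86.6% | 89.2% / 90.2% |

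Standard errors: 0.5–0.6 points for rejection after the switch, 0.8–0.9 for false benefit after the switch, 0.07 for overall error. Switched trials are about 5% of all trials but supply 22%, 21% and 16% of all false positives.

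A smaller simulation with likelihood-ratio tests (480 triggered trials per setting) gave 31.9%, 26.5% and 15.6% false positives after the switch at correlations of about 0, .27 and .51. The default model gave 5.0–6.7% in the same trials.

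**The case against.** The strongest reply is that the damage to the trial as a whole is slight. In simulation the procedure runs at 5.3–5.9%, which is 0.3–0.9 points above nominal. Power stays above .80, nothing changes in about 95% of trials, and the rule is prespecified, uses baseline data only and leaves no discretion after follow-up. All of that stands, and it limits the weight of the point.

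A sharper reply is that the large conditional figures belong to any difference-in-change test in trials selected for baseline imbalance. A fixed model with the main effect would show the same figures in those trials. This is also true. Such a model holds 5% because it is conservative elsewhere: at r = .5, (.05 − .05 × .185)/.95 = 4.3% in the trials without imbalance. The switch takes the high-error part and discards the offset, because the default model runs at 5% in the other trials. The overall excess is that lost offset: .95 × (.05 − .043), or about 0.7 points.

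Three further reservations are fair. The upper ends (34%, 6.4%) need zero correlation between past and later ER use, which is an extreme; the simulated ranges are the better guide. The 5% trigger rate assumes a .05 level, and a stricter level would fire less often. The simulation omits site and covariates, so its figures are approximate.

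Finally, the switch might be defended as protection against faulty allocation. But the chi-square test cannot tell a fault from chance, and a sensitivity analysis shows the same information without altering the primary test.

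**Conclusion.** The point holds. The prespecified procedure for H2 exceeds its nominal two-sided .05 level, by about 0.3–1.4 points on the normal approximation; in simulation it adds 0.6–1.1 points over keeping the default model. The average cost is modest. In the roughly 1 trial in 20 where the rule fires, the cost is serious. With no effect and Living Well higher at baseline, false benefit is declared in 18–26% of trials against 2–3%. With the planned effect and Living Well lower (about 2.5% of trials), power is 15–41% against 84–90%. The rule also discards the precision for which the default model was chosen.

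The sizes depend on an assumed within-person correlation (0 to .8 in the approximation; phi .15 to .45 in simulation), an assumed .05 trigger level and a model without covariates. The direction is the same throughout the range examined. This should be corrected, but it does not undermine the design.

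**What to change.** Before anyone sees baseline ER use by arm, amend the Hypothesis 2 text as follows:

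1. Delete the chi-square test as a decision rule, and delete the switch.
2. State that H2 is tested in all cases with the model that omits the study-condition main effect.
3. Report the model that includes the main effect as a labelled sensitivity analysis. Baseline ER rates by arm can still be tabulated descriptively.

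No data, patients or procedures change. What is given up is an automatic change of primary test if an imbalance comes from faulty allocation; the sensitivity analysis makes that case visible instead.

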In exploratory analyses we will categorize evident causes for emergency room admission and describe and compare the distribution of causes across the 5 chronic medical condition categories using a two-way table with row percentages. Associations between chronic medical condition and cause of emergency room admission will aid us in interpreting results for our ER primary outcome.

Secondary Hypotheses (3 and 4 - regarding more proximal attitudinal and behavioral outcomes):

Hypothesis 3 (H3): Compared to those receiving a general medical illness education and support group, participants receiving Living Well will report improved health-related self-efficacy and patient activation. Further, such improvements will mediate the effects on functional outcomes and ER use.

For self-efficacy and patient activation as outcomes, we will use a parallel model as for Hypothesis 1 to Version 9, 5/1/2015

compare the two study conditions. To test whether change in health-related self-efficacy or patient activation mediates the effect of Living Well we will estimate the mediated effect with a 95% confidence interval. When there is a mediating variable (i.e. mediator), the total effect of treatment can be divided into two components: (1) the direct effect of treatment (independent of the mediator), and (2) the mediated effect (i.e. indirect effect of treatment through the mediator (50). To estimate the mediated effect we will first estimate the total effect of Living Well and second, the direct effect of Living Well, and then estimate the mediated effect by subtracting the second from first. The estimate of the total effect of Living Well will be the treatment effect from the primary analysis model under either H1 or H2. The estimate of the direct effect of Living Well will be the treatment effect of Living Well after adjusting for the mediator. The mediator will be the change score of health-related self-efficacy or patient activation from randomization to post-treatment (for the functional outcomes) or randomization to the 3 month follow-up (for ER use). For statistical inference we will produce a 95% confidence interval around the mediated effect with a bootstrap procedure (51). We will interpret such a 95% confidence interval excluding zero as a statistically significant mediated effect.

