Hypothesis 4 (H4): Compared to those receiving a general medical illness education and support group, participants receiving Living Well will report improved self-management behaviors. Further, such improvements will mediate the effects of the functional and service outcomes specified above.

We will use a parallel model as for Hypothesis 1 to compare the two conditions on the self-management behavior scales at post-treatment. The tests of mediation will be directly parallel to those described for the test of mediation in Hypothesis 3 for the functional and ER use outcome variables.

Secondary Hypothesis 5: Living Well participants will sustain improvements across functional, attitudinal and behavioral outcomes at follow-up (3 months post-treatment).

We will test sustained improvement by testing the null hypothesis of no difference in change from randomization to the 3-month follow-up assessment (2-sided test) which will be the test that the coefficient for the study condition-by-time interaction term in the primary model (see H1) is zero. This hypothesis applies only to outcomes obtained from interview, not for ER visit and other 6-month service utilization variables. All available data will be included in these intent-to-treat analyses. The aforementioned analysis plan regarding dropout will be used.

Exploratory analyses: We will conduct several exploratory analyses.

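### For ER use, subtracting logistic treatment coefficients does not give the mediated effect: it attenuates real mediation and, under some conditions, flags a wrong-sign effect

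*Protocol*

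**What the plan says.** All references are to the protocol, Data Analysis, For Effectiveness Trial.

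- **H2 (ER use).** The model is logistic: "Analysis model (logistic mixed effects model, random intercept not displayed) will be". Its test is on the study-condition-by-time coefficient.
- **H3 (mediation), total effect.** "The estimate of the total effect of Living Well will be the treatment effect from the primary analysis model under either H1 or H2".
- **H3, direct effect.** This is the same treatment effect after adjustment for the mediator, which is a change score for self-efficacy or patient activation.
- **H3, mediated effect.** The plan will "then estimate the mediated effect by subtracting the second from first".
- **H3, decision rule.** A bootstrap 95% interval that excludes zero, on either side, counts as a significant mediated effect.
- **H4 (self-management behaviors).** "The tests of mediation will be directly parallel to those described for the test of mediation in Hypothesis 3", for the functional outcomes and for ER use.

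No other scale, rescaling or estimator is given for the binary outcome.

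**The concern.** In the linear SF-12 model, total minus direct is the mediated effect. In a logistic model it is not. Adding any variable that predicts ER use moves the treatment log-odds ratio away from zero, even if Living Well leaves that variable unchanged. The subtraction therefore mixes mediation with a change of scale, and the scale change works against the mediated effect. ER use is too common here for a rare-outcome approximation to rescue it.

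At stake is the evidence on mechanism for one of the two primary outcomes: whether self-efficacy, activation or self-management carries an effect on ER use. A real mediated effect could be understated and missed, and in some settings an apparent suppression effect could be reported that does not exist.

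**Working it through.** **1. Inputs.** From Sample Size: control ER 25%, Living Well ER 10.7%, two-sided alpha 0.05, power 0.80, 125 per condition, 12% loss of interview data at post-treatment (net 220), and a pilot baseline ER rate of 31.3%. Not in the protocol, so assumed: a mediator–ER odds ratio (OR) of 1.5, 2 or 3 per SD (protective); an effect of Living Well on the mediator of a = 0, 0.2 or 0.4 SD; and the 12% loss holding also at the 3-month follow-up.

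**2. The plan's own figure.** With mean proportion 0.1785:

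n = [1.96·√(2·0.1785·0.8215) + 0.842·√(0.25·0.75 + 0.107·0.893)]² / 0.143² = 111.4, i.e. 112 per arm.

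With continuity correction, (n/4)·[1 + √(1 + 4/(n·0.143))]² = 125.0, i.e. 125 per arm. The stated 250 is reproduced. The protocol gives no figure for the mediation analysis.

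**3. Total effect on the logit scale.** ln(0.107/0.893) − ln(0.25/0.75) = −2.122 + 1.099 = −1.023.

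**4. What the subtraction converges to.** Take logit P(ER) = α + c′·(Living Well) + b·M, with b = −ln(OR), and M normal with SD 1 and mean 0 (control) or a (Living Well). Solve α and c′ so that the arm averages over M are 0.25 and 0.107. Then:

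- subtraction = −1.023 − c′
- true marginal indirect log-OR = logit(0.107) − logit(p*), where p* is the mean ER probability under Living Well with M at its control distribution.

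Example, OR 2 and a = 0.4: b = −0.693, α = −1.210, c′ = −0.815, p* = 0.135. Subtraction gives −0.208, the true marginal effect is −0.263, and a·b = −0.277. Share lost: 1 − 0.208/0.263 = 21%.

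| a (SD) | OR per SD | c′ | total − direct | true marginal | lost |
|---|---|---|---|---|---|
| 0 | 1.5 / 2 / 3 | −1.047 / −1.093 / −1.194 | +0.024 / +0.069 / +0.171 | 0 | – |
| 0.2 | 1.5 / 2 / 3 | −0.966 / −0.954 / −0.975 | −0.057 / −0.069 / −0.049 | −0.080 / −0.132 / −0.193 | 29% / 48% / 75% |
| 0.4 | 1.5 / 2 / 3 | −0.885 / −0.815 / −0.755 | −0.138 / −0.208 / −0.268 | −0.159 / −0.263 / −0.384 | 13% / 21% / 30% |

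Differences were taken before rounding.

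**5. The stated rule at trial size.** 220 participants with mediator data, follow-up logistic model, percentile bootstrap, 800 simulated trials with 399 resamples each. Percentage of trials with an interval excluding zero (for a = 0.2, subtraction counted in the correct direction only):

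| a (SD) | subtraction, OR 1.5 / 2 / 3 | product of coefficients, OR 1.5 / 2 / 3 |
|---|---|---|
| 0 | 4.9 / 12.4 / 22.6 | 2.4 / 4.9 / 5.1 |
| 0.2 | 6 / 9 / 4 | 17 / 28 / 31 |
| 0.4 | 35 / 50 / 38 | 50 / 80 / 84 |

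Under subtraction with a = 0.4, power falls from 50% to 38% when the mediator is made more prognostic (OR 2 to OR 3).

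**6. The planned two-time-point model.** Random-intercept logistic model, assumed intercept SD 1, mediator acting at follow-up, 270 to 346 simulated trials with 199 resamples each.

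- a = 0: subtraction rejects in 10.1% (OR 2) and 21.1% (OR 3), the product in 5.1% and 5.6%.
- a = 0.4, OR 2: 43% against 77%.
- a = 0.2, OR 2: 7.5% against 32%.

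**7. Mediator entered as a main effect at both times.** The large-sample difference with a = 0 is only −0.003 (OR 1.5) to −0.007 (OR 2). With OR 1.5 and a = 0.4 it is −0.057 against a·b of −0.162, so more real mediation is missed.

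**The case against.** Several points can be made for the plan, and most of them stand as limits.

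- **A reader might infer that the rule finds mediation where there is none, as a general property.** The documents do not support that. The excess needs a real direct effect and an association near OR 2 per SD or more. At OR 1.5 the rate is about 5%, and with an unrelated mediator it is at or below 5%. The protocol gives no value for this association.
- **A reader might infer false support for H3 or H4.** Nearly all the false intervals have the suppression sign, opposite to what those directional hypotheses claim. The rule as written does count either side, but false support in the claimed direction is not inflated.
- **The model is not fully stated.** The protocol says only that it adjusts for the mediator. Under plain main-effect entry the false signal nearly vanishes (step 7). The loss of real mediation does not.
- **The bootstrap type is not named.** A Wald-type interval in the mixed model gave lower false-positive rates, about 2% at OR 2 and 7% at OR 3.
- **Subtraction is not wrong in itself.** On the risk-difference scale, total minus natural direct equals the natural indirect effect exactly. The fault is the log-odds scale. The H3 text speaks of the treatment effect without naming that scale, and a separate analysis plan could fix another. But it takes that effect from the H2 model, whose tested effect is a logit coefficient, so the protocol as written subtracts logit coefficients.

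**Conclusion.** The point holds in a limited form. For ER use in H3 and H4 the stated estimator does not estimate the mediated effect. The consistent consequence is attenuation, which appeared at every association examined with the mediator acting at follow-up and also in the main-effect case checked. With a 0.4 SD mediator effect, 13% to 30% of the indirect effect is lost and power is 35% to 50% where a product of coefficients would have 50% to 84%. Wrong-sign false flags (about 5%, 12% and 23% at OR 1.5, 2 and 3) are a second, conditional consequence.

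That the subtraction is wrong on this scale is certain. The sizes are not: they rest on the assumed associations, a normal mediator, 220 participants with mediator data, a percentile bootstrap and, for the mixed model, an intercept SD of 1. The reach is one outcome within secondary mediation tests. The H1 and H2 tests and the SF-12 mediation are untouched, so the point should be corrected but does not threaten the primary analyses.

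**What to change.** For ER use in H3 and H4:

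1. Replace the subtraction of logit coefficients with one of two estimators, keeping the planned bootstrap interval. One is a product of coefficients: the treatment effect on the mediator times the mediator coefficient in the mediator-adjusted logistic model. The other is a natural indirect effect on the risk-difference scale: the difference in mean predicted ER probability under Living Well with the mediator at its Living Well and at its control level.
2. State how the mediator enters the two-time-point model, and let it act on follow-up ER use (mediator-by-time).
3. Fit the models on the same participants. ER use comes from charts for everyone randomized, but the mediator exists only for those interviewed.
4. Count as support for H3 or H4 only an interval that excludes zero in the hypothesised direction.

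Keep total minus direct for the linear SF-12 outcomes.

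The product has the better-documented error rate here (2.4% to 5.6%). In a smaller check of the risk-scale effect (300 simulated trials, 125 per arm, follow-up-only model, 1.0 to 1.5 log-odds per SD) it rejected in about 9% of trials without mediation. If it is chosen, its interval should first be checked by simulation.

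The cost is a paragraph of wording and a few lines of code. No new data and no change to sample size or conduct are needed.

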#### Data Analysis

##### FOR EFFECTIVENESS TRIAL:

Primary Hypotheses (regarding functional and service-related outcomes):

Hypothesis 1 (H1): Compared to those receiving a general medical illness education and support group, participants receiving Living Well will demonstrate greater improved general health functioning including both physical and emotional functioning.

To test the null hypothesis of no difference in improved general health functioning, we will use a longitudinal mixed effects model to compare change in mean physical and emotional health functioning from randomization to post-treatment. Regression equation (random effects not presented) at each time point will be:

SF12 function = Intercept + site + covariates + study condition + time + study-condition\*time + error

Notes: (1) Test of the null hypothesis of no difference in change from randomization to the post-treatment assessment will be conducted using a specified contrast. (2) "Study condition" is a dichotomous variable indicating study condition; (3) A random intercept and random slope (coefficient for time) will also be specified for the model; (4) The "time" variable will be entered as a continuous variable with possible values 0, 3, and 6 corresponding to the three assessment points (randomization, post-treatment, & 3-month follow-up); (5) The "covariates" terms represent adjustment for age, race, gender, and important potential confounders and will include Charlson comorbidity index score, chronic somatic illness

category, and any other covariate found to significantly differ at randomization (provided no significant collinearities are found). We are expecting few chance differences at randomization due to large sample size and random study condition assignment; (6) We have included a “site” term to adjust for site differences.

Hypothesis 2 (H2): Compared to the medical illness education and support group, the Living Well group will have a lower proportion of participants who will have had an emergency room visit for management of a chronic medical condition during the six months after randomization.

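### H3/H4 mediation on SF-12: adjusting for a per-person change score, read as a covariate with no time interaction, cannot move the condition-by-time effect, so mediation cannot be detected

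*Protocol*

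**What the plan says.** All references are to the Protocol, Data Analysis, effectiveness trial.

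- **The H1 model.** SF-12 function is regressed on site, covariates, study condition, time and condition-by-time. Note (3): "A random intercept and random slope (coefficient for time) will also be specified for the model". Note (4): time "will be entered as a continuous variable with possible values 0, 3, and 6".
- **The H1 effect.** Note (1): "Test of the null hypothesis of no difference in change from randomization to the post-treatment assessment will be conducted using a specified contrast".
- **How adjustment is used.** Note (5): the covariate "terms represent adjustment for age, race, gender, and important potential confounders". These enter the equation without a time interaction. Note (6) uses the same verb for the site term.
- **Total effect (Hypothesis 3).** "The estimate of the total effect of Living Well will be the treatment effect from the primary analysis model under either H1 or H2".
- **Direct effect.** "The estimate of the direct effect of Living Well will be the treatment effect of Living Well after adjusting for the mediator".
- **Mediator for the functional outcomes.** "The mediator will be the change score of health-related self-efficacy or patient activation from randomization to post-treatment".
- **Decision rule.** The mediated effect is total minus direct, and it is called significant if a bootstrap 95% interval excludes zero.
- **Hypothesis 4.** "The tests of mediation will be directly parallel to those described for the test of mediation in Hypothesis 3".

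No equation is given for the direct-effect model, and no mediator-by-time term is mentioned for H3 or H4.

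**The concern.** The SF-12 treatment effect is a difference in slopes. The mediator is a single number per person, constant across that person's visits. Entered like the other covariates, it can explain why some participants sit higher or lower on SF-12 throughout, but not why some improve faster. Subtracting two estimates of the same slope difference then says nothing about mediation.

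Mediation is an explicit half of both H3 and H4. If the SF-12 analysis is run this way, it would report no mediation through self-efficacy, activation or self-management behaviors even if these carried the whole effect. That would be a false negative about how the intervention is supposed to work.

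**Working it through.** The protocol states no figure for the mediated effect, so there is none to reproduce. The inputs taken from it are the H1 model with time at 0, 3 and 6, and the Sample Size section's 12% loss at post-treatment (250 × 0.88 = 220). Effect sizes, variances and month-6 loss below are assumptions.

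**1. The model in two equations.** Let Z be condition, X the site and covariate terms, and M the mediator change score. For participant i, Y(t) = a_i + b_i·t + error, with

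- intercept: a_i = α0 + α1·Z_i + α2·X_i + γ·M_i + u0_i
- slope: b_i = β0 + β1·Z_i + u1_i

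The H1 contrast from month 0 to month 3 is 3·β1. A mediator entered as a covariate adds γ·M to the intercept equation only.

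**2. Complete data.** Each participant's fitted slope is (−3·Y0 + 0·Y3 + 3·Y6)/18 = (Y6 − Y0)/6. The slope equation's regressors (1, Z) are a subset of the intercept equation's (1, Z, X, M). In such a pair of equations, generalized least squares for the smaller one equals ordinary least squares, whatever the covariance of u0 and u1. Hence

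3·β1 (estimated) = ½ × [mean(Y6 − Y0) in Living Well − mean(Y6 − Y0) in control].

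M does not appear, so total − direct = 0. Re-estimated variance components make no difference, because the estimate does not depend on them.

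**3. With mediator-by-time added.** The slope equation becomes b_i = β0 + β1*·Z_i + λ·M_i, and total − direct = 3·(β1 − β1*) = 3·λ × (between-arm difference in mean M). This is the mediated effect.

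**4. Example.** Take a mediator effect of 0.5 SD and 3·λ = 0.80, so the fully mediated effect at month 3 is 0.80 × 0.5 = 0.40 SD. The covariate-only reading gives 0.40 − 0.40 = 0.00; with mediator-by-time it is 0.40 − 0 = 0.40. If half is mediated, the answers are 0.00 and 0.20. Simulated trials (n = 220, linear change) gave these values. The covariate-only difference was at most about 2e-15 in complete data, with the random-effects correlation at −0.3, 0 or 0.3.

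**5. Attrition.** Simulation of 1,000 trials per scenario, n = 250, true mediated effect 0.60 points, generalized least squares with known variances:

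| Scenario | Covariate only: total on everyone, direct on those with a mediator score | Covariate only: same participants | Mediator-by-time: same participants |
|---|---|---|---|
| Complete | 0 | 0 (max 1.9e-14) | 0.603 |
| 12% lost at month 3 | mean −0.0003, SD 0.081 | 0 (max 1.4e-14) | 0.605 |
| As above, plus about 12% outcome-dependent loss at month 6 | mean 0.0015, SD 0.088 | mean 0.00001, SD 0.011, max 0.045 | 0.604 |
| About 20% lost at month 6 only | mean 0.0000, SD 0.014 | mean 0.00001, SD 0.014, max 0.056 | 0.604 |

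A fitted REML model on complete data (40 trials) gave 0 for covariate-only and 0.616 with mediator-by-time.

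**6. ER use.** The H2 model has no condition main effect, so steps 1 and 2 do not carry over. In 60 simulated trials under one assumed set of values, the total log odds ratio averaged −0.71. The mediated part averaged −0.15 with the mediator as a covariate and −0.34 with mediator-by-time. It is smaller, but not zero.

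**The case against.** **The protocol does not say that the mediator enters as a main effect only.** This is true, and it is the strongest objection. The team also clearly knows how a person-level variable acts on change: the exploratory analyses name a dose-by-time term and three-way terms with time. One could argue that splitting a condition-by-time effect implies the matching interaction. But those same passages show that by-time terms are named when wanted, none is named for H3 or H4, and adjustment in the H1 notes means terms without one. The covariate-only reading is a strong inference, not stated text.

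**This belongs in a statistical analysis plan.** One may exist and settle it. Yet the protocol itself fixes the primary model, the mediator, the subtraction and the decision rule. Followed in its own vocabulary, that text gives a method that cannot work for SF-12.

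**A reader might infer that the result is always exactly zero.** The documents do not support that. The protocol expects 12% loss at post-treatment, just when the mediator is measured, and takes the total effect from the primary model. Total and direct may then rest on different participants, and the difference becomes noise around zero. The noise carries no mediation information, so the method is not rescued. It does make the failure harder to see: a zero-width bootstrap interval from complete data would be noticed at once, whereas an interval spread around zero looks like an ordinary null result.

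**A reader might infer that all H3 and H4 mediation testing fails.** It does not follow, because mediation of ER use rests on the H2 model, where the estimate does move.

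**Conclusion.** The point holds for the SF-12 part of the H3 and H4 mediation tests, on the natural reading that the mediator is adjusted for like any other covariate. On that reading total minus direct is exactly zero with complete data, and this does not depend on effect size, variances or random-effects covariance. With attrition it averages zero, with SD from effectively 0 to 0.088 points in the scenarios tried, against an assumed true 0.60. Those SDs depend on the assumed variances and dropout patterns. If the intended model already includes mediator-by-time, the defect is one of wording only. The primary H1 and H2 tests and the direct comparisons on self-efficacy, activation and behaviors are unaffected.

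**What to change.** State, for SF-12 under H3 and H4:

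- The direct-effect model is the H1 model plus the mediator change score and its interaction with time. The direct effect is the same randomization-to-post-treatment condition contrast as in H1.
- The total-effect and direct-effect models are fitted on the same participants, those with a mediator change score, within each bootstrap sample. The bootstrap interval and decision rule stay as they are.

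Regressing the 0-to-3-month SF-12 change on condition, with and without the mediator, may look like a simpler substitute. It is a different estimator: with complete data the linear-time contrast is half the 0-to-6-month change and gives month 3 no weight. The two agree in expectation only if change is linear.

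The cost is a few sentences and no new data. The downside is that the total effect used for mediation comes from participants with a mediator score and may differ slightly from the primary H1 estimate. The sentence equating the two needs amending for SF-12, and both figures should be reported.
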